3. Client's (qualitative) views on individual therapy sessions assessed with the Helpful Aspects of Therapy form (HAT; Lewlyn, Elliott, Shapiro, Firth, & Hardy, 1988). Completed by therapist in discussion with participant.

Fidelity measure

1. Adherence to ACT related processes assessed with the ACT Fidelity Measure (ACT-FM; O'Neill, Latchford, McCracken & Graham, 2019). Completed by therapist and secondary researcher.

EXPLORATORY OUTCOMES

Adaptations made to treatment will be recorded so that commentary can be made on what adaptations to ACT may be beneficial for older adult clients. **Consideration of the impact that delivering the intervention in a remote manner will also be made and any adaptations that were made to facilitate this.**

TABLE OF OUTCOMES

Objectives	Outcome Measures	Timepoint(s) of evaluation of this outcome measure (if applicable)
Primary Objectives	1. Quality of life (OPQOL-brief).	1. Baselines, pre-, mid- and post-intervention, and at six-week follow up.
Secondary Objectives	Symptom measures 1. Cognitive functioning (MoCA). 2. Changes in levels of anxiety and depression (HADS).	1. At initial contact, by service as standard practice. 2. At initial contact, by service as standard practice. Baselines, pre-, mid- and post-intervention,

		and at six-week follow up.
	Change measures 
 1. Client's goals (PQ). 2. Client's view on change (Change Interview). 	
 1. Prior to each weekly treatment session. 2. One week after finishing treatment.
	Process measure 
 1. Psychological flexibility (CompACT-8). 	
 1. Baselines, pre-, mid- and post-intervention, and at six-week follow up.
	Session measures 
 1. Quality of life/general outcomes (ORS). 2. Therapeutic alliance (SRS). 3. Client's views on the therapy session (HAT). 	
 1-3. At the end of each weekly treatment session.
	Fidelity measures 
 1. Fidelity of treatment (ACT-FM). 	
 1. At the end of each session (by therapist) and random sampling of all sessions (by Secondary Research Supervisor).

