To facilitate the cross-referencing of rich case records, several methods of analysis will be employed, dependent on the evidence area required for the affirmative or sceptic brief. These are outlined in Tables 1 and 2, respectively. All analyses will be completed using SPSS (Version 25.0; IBM Corp, 2017) or Microsoft Excel (Version 15.0.5179.1000; Microsoft Corporation, 2013). Analyses will be performed by the student researcher/therapist either at the MHSOP or the Universities of Lincoln or Nottingham. No data containing confidential information will be analysed outside of the MHSOP, in line with relevant NHS Trust policies.

Table 1		
Direct evidence for links between therapy process and outcome, from Elliott (2002).		
Direct evidence area	Description	Method of evaluation (specific analysis method)
1. Retrospective attribution	Change attributed by client to the therapy	Content of Change Interview (Framework Analysis)
2. Process-outcome mapping	Content of post-therapy changes correspond to specific processes within therapy	Correlations between within therapy measures (HAT), and quantitative outcome measures (Pearson correlation, or Spearman correlation if assumptions of normal distribution not met).
3. Within-therapy process-outcome correlation	In-therapy process variables covary with week-to-week changes in client problems	Correlations between ACT adherence and ORS, and the change questionnaire (i.e. the SPQ; Pearson/Spearman correlation)
4. Early change in stable problems	Therapy coincides with changes in long-standing client problems	Change in outcome measures from baseline to initial sessions (Pearson/Spearman correlation, visual analysis)
5. Event-shift sequences	Important events precede stable shifts in client problems, especially if therapy process and client change are logically related	Correspondence between within therapy measure (HAT) and variation in patient's problem (SPQ; Pearson/Spearman correlation, visual analysis)

Note: HAT – Helpful Aspects of Therapy form. SPQ – Simplified Personal Questionnaire.

Table 2

Evidence for links between nontherapy processes and outcome, from Elliott (2002)

Nonchange/ nontherapy area	Changes are...	Method of evaluation (analysis method)
1. Non-improvement	Either trivial or negative.	Assess reliable and clinical significance on measures (RCI calculations); ask ppt the importance and direction of any change (Change Interview).

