2. Statistical artefacts	Reflect measurement error, outlier to the mean, or experimentwise error.	Assess for reliable change (RCI calculations); stability of client problems through multiple baselines (Pearson/Spearman correlation, visual analysis); replication of change over multiple measures (RCI calculations).
3. Relational artefacts	Superficial artefacts related attempts to please therapist/researcher.	Evaluate client social desirability and determine covariance with measures (ANCOVA); ask ppt their negative and positive descriptions of therapy (Change Interview).
4. Client expectations	Related to expectations or wishful thinking.	Assess client expectations at start; ask ppt whether changes were expected or surprising (Change Interview).
5. Self-correction	Reflect self-help or self-initiated remedy of temporary problems.	Determine direction and stability of measures from baseline to initial sessions (Pearson/Spearman correlation); ask ppt duration of problems using SPQ; look for self-help efforts begun before therapy via demographics form and assessment.
6. Extra-therapy life events	Attributed to life events, e.g., changes in clients' situation.	Monitor for such events; assess likelihood of change without therapy (Change Interview); consider mutual influence these factors have on each other.
7. Psychobiological factors	Attributed to medication, medical illness recovery etc.	Collect information on medication and physical health prior to, and during therapy.
8. Reactive effects	Due to being in research, sense of altruism in client, relationship with researcher.	Ask client directly about effects of research (positive and negative); use of external ratings; minimise research impact.

Note: ANCOVA – Analysis of Covariance; RCI – Reliable Change Index (Jacobson & Truax, 1991); SPQ – Simplified Personal Questionnaire (Elliott, Mack, & Shapiro, 1999); ppt – participant.

STUDY SETTING

The study will be a single centre study, run from a Mental Health Service for Older People (MHSOP) at Lings Bar Hospital, Nottinghamshire.

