As standard practice for psychology referrals at the MHSOP, the initial assessment will be completed primarily by [name], the Field Research Supervisor for the study. [name] will then screen psychology referrals for appropriate participants and inform them about the study. Following social distancing restrictions in place due to the SARS-CoV-2 outbreak, the MHSOP is currently only offering face-to-face appointments when necessary, offering telephone or videocall therapy appointment as a standard replacement. As such, the therapy in the current study will be offered by either telephone or videocall. At first contact, participants will be asked their preference and what technology provisions they have to facilitate videocalling (i.e. a smartphone or a laptop/PC with microphone and camera). The sessions will then be conducted using QHealth (MyMed Ltd, 2020), which is an NHS Digital and NHS England approved, centrally funded eConsultation supplier for the COVID-19 response. The therapeutic intervention will be conducted by the student researcher/therapist, [name]. Clinical supervision will take place between student researcher/therapist and [name] at the MHSOP. Weekly ACT supervision will be conducted between student researcher/therapist and Secondary Research Supervisor via telephone or face-to-face.

SELECTION OF PARTICIPANTS

ELIGIBILITY CRITERIA

To be eligible for the study, participants must have first been referred to the MHSOP for psychological support. The study will recruit both male and female participants, aged 65 years or older (there is no upper age limit).

Inclusion Criteria

1. Be at least 65 years of age.
2. Score at least 8 on the Hospital Anxiety and Depression Scale (HADS; Zigmond & Snaith, 1983) on either the anxiety or depression sub-scale. The HADS is an outcome measure already used by the MHSOP.
3. Be referred to the MHSOP for psychological support.
4. Have capacity to give informed consent.
5. Be willing to engage in one-to-one psychotherapy over telephone or videocall.

Exclusion Criteria

1. A score lower than 22-24 on the MoCA. This is to screen for a level of cognitive deficit, which cannot be accommodated for in the current study, due to the adaptations which will be required (e.g. review sessions, carer enrolment to support memory consolidation). Cut-off limit is dependent on the individual's age and education history. The MoCA is administered by the MHSOP as standard practice.

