At the time of recruitment, all potential participants will be active referrals at the Rushcliffe Mental Health Service for Older People (MHSOP), Lings Bar Hospital, Nottinghamshire. They will also have been referred for further psychology support (i.e. any referral that is felt would benefit from individual clinical psychology sessions). Eligible clients (see inclusion/exclusion criteria) will be informed (through discussion and Participant Information Sheet) about the study during a psychology referral assessment with a Clinical Psychologist from the MHSOP ([name], Field Research Supervisor for the study), delivered by phone/videocall due to social distancing requirements. Adaptations such as larger font on sheets will be determined as well as whether they would be able to facilitate videocall therapy. Potential participants that are interested in taking part will have the CF and PIS posted out to them, with a follow-up call around a week later to obtain consent. Clients that do not consent to take part will be offered usual care from the service.

The Assistant Psychologist from the team will call those participants that consent to determine the dates of the intervention. The Assistant Psychologist will also go through a pack of questionnaires (Questionnaire Pack 1.1 [QP1.1]), which will have been posted out to them. This date will act as Baseline 1. The Assistant Psychologist will then call back a following three times, acting as Baselines 2, 3, and 4, all a week apart. Baseline 4 will ideally be the same day as the start of the Acceptance and Commitment Therapy (ACT) intervention. The ACT intervention will be conducted by the student researcher/therapist via telephone or videocall, depending on the participants wishes. Sessions will be audio recorded using an NHS encrypted electronic device, with participant knowledge, to conduct fidelity checks of the treatment at a later date. Participants will be supported to complete questionnaires after the session which will have been posted out to them.

Therapeutic sessions

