Data from throughout the study will be cross-referenced to develop the affirmative and sceptic briefs required for the HSCED. Pseudonyms will be used for the participants and there will be no patient identifiable information within the briefs. Once completed, the briefs will be sent to the expert panel of three Clinical Psychologist, with relevant interest and experience of psychotherapeutic change methods. The panel adjudicate over the case material using a semi-structured questionnaire to decide whether the client made a substantial change and where they attribute this towards (ACT-specific, non-specific, or extra-therapeutic factors). This process allows for a reduction in researcher bias.

SCHEDULE OF PROCEDURES

Procedures	Visits									
	Psychology Screening Assessment & Baseline 1 (wk1)	Baseline 2 (wk2)	Baseline 3 (wk3)	Baseline 4 & Session 1 - pre (wk4)	Sessions 2-5 (wks 5-8)	Session 6 - mid (wk 9)	Sessions 7-11 (wks 10-14)	Session 12 - post (wk 15)	Change Interview (wk 16)	Six wk follow-up (wk 20)
Informed consent	x									
Symptom, & process measures	x	x	x	x		x		x		x
Demographics	x									
Medical history	x						x			
ACT intervention				x	x	x	x	x		
Session, change, & fidelity measures				x	x	x	x	x		
Change Interview									x	

Note: wk = week; see Timetable of Measures for outline of when individual measures are administered.

WITHDRAWAL

Participants may be withdrawn from the trial either at their own request or at the discretion of the Investigator. The participants will be made aware that this will not affect their future care. Participants will be made aware (via the information sheet and consent form) that should they withdraw the data collected to date may not be erased in accordance with the University's Research Privacy Notice and information given in the Participant Information Sheet and may still be used in the final analysis.

Stopping rules and discontinuation:

- If a participant withdraws consent to continue.
- If a participant expresses that the intervention is causing their anxiety and depression to get worse.
- If a participant's physical health significantly deteriorates to a point where continuation would be impractical or create sufficient negative burden on them.
- If a participant fails to comply with the intervention.
- If new findings become published regarding likely risks or negative effects of ACT.

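### No measure is scored repeatedly both at baseline and in the early sessions, and the weekly problem measure (SPQ) has no baseline series

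*Combined protocol and SAP*

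**What the plan says.** Three rows of the DATA ANALYSIS tables rely on scores around the start of therapy.

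- Table 1 row 4 (early change in stable problems): "Change in outcome measures from baseline to initial sessions", by Pearson or Spearman correlation and visual analysis.
- Table 2 row 5 (self-correction): "Determine direction and stability of measures from baseline to initial sessions", by correlation only. It adds the reported duration of problems and a search for self-help begun before therapy.
- Table 2 row 2 (statistical artefacts): "stability of client problems through multiple baselines", by correlation and visual analysis, alongside reliable change calculations.

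Timing is given in the TABLE OF OUTCOMES, the STUDY REGIMEN and the SCHEDULE OF PROCEDURES, which agree. OPQOL-brief, HADS and CompACT-8 are taken at four weekly baselines, at mid-therapy (usually session 6), at the final session and at follow-up. The fourth baseline shares a column with the start of therapy: "Baseline 4 & Session 1 - pre (wk4". The SPQ is first completed at session 1, before ACT is introduced, and then before each session. The ORS is completed at the end of each session. For HADS the outcome table reads "At initial contact, by service as standard practice. Baselines, pre-, mid- and post-intervention", so there may be one earlier score. The schedule's note also says "see Timetable of Measures for outline of when individual measures are administered"; that timetable is not in the supplied text.

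**The concern.** The study is a series of up to four single cases with no control arm. Its second guiding question, whether change can be attributed to ACT, therefore depends partly on whether improvement was already under way before session 1. Table 2 row 5 exists to test that rival explanation, and Table 1 row 4 is its affirmative counterpart.

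A comparison across the start of therapy is most informative when one measure is repeated on both sides. The SPQ is the measure Table 1 uses for week-to-week change in the client's own problems, so it is the natural candidate. If it has no run of scores before therapy, the adjudicators cannot see whether those problems were stable, improving or fluctuating when ACT began. A pre-therapy series cannot be recovered once a participant has started.

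**Working it through.** **Step 1: count the scores.** The schedule puts session 1 in week 4, session 6 in week 9 and session 12 in week 15, so session s falls in week s + 3. The plan does not define initial sessions, so three readings are shown.

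| Measure | Before ACT starts | After, through session 3 | Through session 5 | Through session 6 |
|---|---|---|---|---|
| OPQOL-brief, CompACT-8 | 4 (weeks 1-4) | 0 | 0 | 1 |
| HADS | 4, or 5 with the initial-contact score | 0 | 0 | 1 |
| SPQ | 1 (week 4) | 2 | 4 | 5 |
| ORS | 0 | 3 | 5 | 6 |

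Under every reading, no measure has two or more scores in both columns. The extra HADS score adds only to the baseline side. The regimen places the assessment before Baseline 1 ("with a follow-up call around a week later to obtain consent"), although the grid puts both in week 1. It also appears to be the entry score ("Score at least 8 on the Hospital Anxiety and Depression Scale"), so selection may have raised it.

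**Step 2: what the SPQ can and cannot show.** Take score = b0 + b1 × week + b2 × max(week − 4, 0) + error. Here b1 is the trend already under way and b2 the change of slope at therapy start. From week 4 onward, max(week − 4, 0) = week − 4, so the third column equals the second minus 4 times the first. The design has rank 2 for 3 parameters on weeks 4-8, and still on weeks 4-15. More sessions do not help. Early change can be plotted from the single starting score, but b1 and b2 cannot be told apart.

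**Step 3: what the other measures can show.** I assume the same model with independent errors of equal SD, and a two-sided 5% level for power. SE is in error-SD per week; half-width = t(0.975, n − 3) × SE.

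| Series | SE of b2 | df | 95% half-width | Power at 0.5 / 1.0 error-SD per week |
|---|---|---|---|---|
| OPQOL-brief or CompACT-8, weeks 1-4 and 9 | 0.623 | 2 | 4.303 × 0.623 = 2.68 | not computed |
| Same, weeks 1-4, 9 and 15 | 0.501 | 3 | 3.182 × 0.501 = 1.59 | 11% / 29% |
| SPQ if also rated in weeks 1-3, weeks 1-8 | 0.618 | 5 | 2.571 × 0.618 = 1.59 | 10% / 26% |
| Same, weeks 1-15 | 0.394 | 12 | 2.179 × 0.394 = 0.86 | 22% / 65% |

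The existing three measures thus allow a before/after slope comparison, imprecisely, and over the whole of therapy rather than early in it. The extended SPQ series is no more precise through week 8.

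**Step 4: correlation over four baselines (Table 2 row 2).** The plan does not say what is correlated with what, and gives no significance level. If it is score against week at two-sided 0.05, Pearson needs |r| of at least 4.303 / √(2 + 4.303²) = 0.950. The smallest exact Spearman p is 2/4! = 2/24 = 0.083. The slope SE is 1/√5 = 0.447 error-SD per week, and power for a drift of 0.5 per week is about 11%. On those assumptions a non-significant r says almost nothing about stability.

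**The case against.** The plan never demands repeated scores of one measure in both phases. Table 1 row 4 can be carried out literally on the SPQ, from its single pre-ACT score. That is true, but a single starting score cannot show direction or stability before therapy, which Table 2 row 5 asks for.

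A reader might infer that the study cannot tell whether improvement began before therapy, or that self-correction would rest mainly on recalled duration and self-help history. The documents do not support this. The primary outcome, the symptom measure and the process measure each have four weekly pre-therapy scores that bear directly on the question. Over therapy as a whole they also have repeated scores, at weeks 9 and 15. The Change Interview, which is to assess how likely change was without therapy, contributes as well.

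The case that this is an interpretive design, judged by a panel and not by a significance test, also stands. Row 2 already names visual analysis and reliable change, and the figures in Step 4 rest on assumptions the plan does not state. They warn against one misreading; they do not show that row 2 fails. The missing timetable could add timepoints, though it would have to depart from three sources that agree.

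**Conclusion.** The point holds in limited form. In the schedule supplied, no measure has repeated scores in both the baseline and the initial sessions, so the comparison in Table 1 row 4 and the quantitative part of Table 2 row 5 cannot be made as worded with repeated data on both sides. The inability to separate a prior trend from change at therapy start applies to the SPQ only. So does the inability to check problem stability over several baselines.

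This touches one of five affirmative areas and parts of two of eight sceptic areas. Evidence in two affirmative areas is enough for adjudication, so a weak row 4 does not block it.

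The score counts rest on the three timing sources and hold whether the initial sessions run through session 3, 5 or 6. The precision figures assume independent, equal-variance errors and a straight trend with one bend at week 4. It would be wrong to conclude that extending the SPQ yields a powered test. Its gain is that the pre-therapy trend on the client's own problems becomes visible and estimable.

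**What to change.** (a) Elicit the SPQ items at the Baseline 1 call and have the participant rate them at the four existing baseline calls (at Baseline 4, before session 1). Continue the same items weekly. Give the adjudicators the plotted series for visual and descriptive use, not as a powered test.

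(b) For OPQOL-brief, HADS and CompACT-8, restate the comparison as baseline to mid-point (about week 9).

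(c) Add visual analysis to Table 2 row 5. State that a non-significant correlation over four baseline points is not evidence of stability.

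(d) If the schedule cannot change, say in Tables 1 and 2 that early change on the SPQ rests on one pre-ACT score, and that no measure has repeated scores in both the baseline and the initial sessions (sessions 1-5). Without that definition the statement would be wrong for OPQOL-brief, HADS and CompACT-8, which are repeated over therapy as a whole.

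Option (a) needs no extra visits. It lengthens four calls already planned, by an amount the documents do not allow one to state, and adds some of the questionnaire burden the plan tries to limit. The Assistant Psychologist would elicit the items, whereas the plan specifies therapist guidance. The administrator, though not the rater, would change at week 4, and the sceptic brief should record that as a possible source of a shift. A protocol amendment is needed, with ethics approval where required. Options (b) to (d) change only wording and reporting.

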2. Not rated higher than Cluster 8 (Mental Health Clustering Booklet 2013/14, Department of Health), a categorisation based on the Health of the Nation Outcome Scale (HoNOS; Wing et al., 1998). Clusters higher than 8 are associated with clients presenting with symptoms of psychosis and it is felt that this level of mental health problem would cause serious heterogeneity between client cases. As standard practice, the MHSOP at Ling Bar Hospital will have rated the client prior to consideration for the study.

3. Inability to understand English to a level required to participate fully in the intervention. This is due to a lack of ability to benefit from the intervention without an interpreter, and the impact an interpreter would have on the non-therapeutic processes (e.g. alliance) being measured in this study.
4. Not currently undertaking any other psychological therapy, talking therapy or counselling. This is due to the potential impact the other therapy could have on change and the inability to fully account for this.

Sampling and size of sample

The study will recruit up to four participants. Most Hermeneutic Single Case Efficacy Designs (HSCED) focus on one client (Stephen, Elliott, & Macleod, 2011). However, there have been recent calls to increase cross case synthesis to further validate the intervention being used (MacLeod, Elliott, & Rodgers, 2012). Three cases would fit with established guidelines for a single-case research series (Smith, 2012) and has shown to be feasible in previous HSCED research (e.g. Wall, Kwee, Hu, & McDonald, 2017). Drop-out or withdrawal would be a major concern with the current study, due to the extended participant contact time and the constraints on recruiting and treating further participants within schedule for Doctoral Thesis submission. With dropout rates around 25% (Grover, Dua, Chakrabarti, & Avasthi, 2018) recruiting up to four participants appears a sensible approach. **A fourth participant will only be recruited up until July 2020, to allow for the completion of the intervention and requirements of submission for the Doctoral Thesis.**

Sampling technique

The sample will be referrals from the MHSOP recruited in a convenience sampling method. As this study aims to reflect usual clinical practice, this is an adequate sampling method to recruit participants.

RECRUITMENT

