The final session will also cover a summary of the sessions, as well as providing the participant with a therapy blueprint of what they specifically found useful. This will include any next steps for the participant (e.g. whether they will continue to be seen by the MHSOP) and what the process is for them to follow if there is a deterioration in mental health. The participant will be reminded of the data processing details and asked again if they would like a summary of the findings from the study.

One week after the final session, participants will complete a Change Interview, facilitated by [name], Trainee Clinical Psychologist, either face-to-face or by telephone/videocall, depending on the social distancing restrictions at the time. The Change Interview is a semi-structured interview to determine whether the client experienced change during the treatment, what they attributed this towards (e.g. therapeutic factors, external factors). The Change Interview is completed by a member of the research team the participant has not had previous contact with (to encourage more honest responses), and will be recorded on a NHS encrypted device so that the answers can be transcribed at a later date. The participants will then receive reimbursement towards their travel (if applicable) and for the factors of research which were additional to normal clinical treatment (extra questionnaires, attending Change Interview).

One month following the Change Interview, participants will be called up again by the Assistant Psychologist to complete QP 1.1. This will act as six-week post-therapy follow-up.

Following final therapy sessions, a secondary member of the research team (likely to be the Chief Investigator) will complete fidelity checks to ensure that the modality (ACT) is sufficiently adhered to. This will be conducted using a random sampling method and the researcher will have access to anonymised audio files, stored on an encrypted NHS Trust device.

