Deviations from the overall study protocol which are found to frequently recur are not acceptable, these will require immediate action and could potentially be classified as a serious breach.

DATA PROTECTION AND PATIENT CONFIDENTIALITY

All study staff and investigators will comply with the principles of the Data Protection Act (2018) in protecting the rights of study participants with regards to the collection, storage, processing and disclosure of personal information and will uphold the Act's/Regulations core principles.

Each participant will be assigned a study identity number, for use on CRFs other trial documents and the electronic database.

Personal data, research data and the linking code will be stored in separate locations. When stored electronically, this will include using encrypted digital files within password protected folders and storage media. Personal information shall be stored separately to research data and will be kept secure, and maintained.

Personal data will be stored for six months following the end of the study, so that the Chief Investigator may provide participants with a summary of the research (should they wish to receive a copy).

Data generated as a result of this study will be available for inspection on request by the participating physicians, the University of Lincoln representatives, the REC, local R&D Departments and the regulatory authorities.

INDEMNITY

Insurance and indemnity for trial participants and trial staff is covered within the NHS Indemnity Arrangements for clinical negligence claims in the NHS, issued under cover of HSG (96)48. There are no special compensation arrangements, but trial participants may have recourse through the NHS complaints procedures.

The University of Lincoln as research Sponsor indemnifies its staff, research participants and research protocols with both public liability insurance and clinical trials insurance.

ACCESS TO THE FINAL DATASET

In compliance with the ICH/GCP guidelines, regulations and in accordance with the University of Lincoln Code of Practice for Research, the Chief or local Principal Investigator will maintain all records and documents regarding the conduct of the study. These will be

retained for at least five years or for longer if required. If the responsible investigator is no longer able to maintain the study records, a second person will be nominated to takeover this responsibility.

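### Exclusion criteria 2 and 4 are worded the wrong way round against their own stated reasons, and the six-week follow-up is scheduled five weeks after the last session

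*Combined protocol and SAP*

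**What the plan says.** **Eligibility.** The Exclusion Criteria have four items. Items 1 (a MoCA score below the cut-off) and 3 (insufficient English) describe people to be kept out. Item 2 is "Not rated higher than Cluster 8 (Mental Health Clustering Booklet 2013/14, Department of Health", and its reason is that "Clusters higher than 8 are associated with clients presenting with symptoms of psychosis", which would make the cases too heterogeneous. Item 4 is "Not currently undertaking any other psychological therapy, talking therapy or counselling", and its reason is "the potential impact the other therapy could have on change and the inability to fully account for this".

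**Follow-up.** The Table of Outcomes lists the OPQOL-brief at "Baselines, pre-, mid- and post-intervention, and at six-week follow up". The Study Regimen puts the Change Interview one week after the final session, then says: "One month following the Change Interview, participants will be called up again by the Assistant Psychologist to complete QP 1.1". It adds: "This will act as six-week post-therapy follow-up". The Schedule of Procedures has session 12 at week 15, the Change Interview at week 16 and the follow-up, again labelled six-week, at week 20.

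**Travel.** The eligibility row of the Study Summary requires ability to travel to the service. None of the five Inclusion Criteria does, and the fifth specifies telephone or videocall therapy.

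**The concern.** An exclusion list is applied by asking whether each statement is true of the client and, if so, turning the client away. On that procedure, items 2 and 4 turn away the clients the study wants and admit those it means to keep out. Concurrent therapy matters particularly here: in a single-case design it is a rival explanation for change, and the protocol says it cannot be fully accounted for. Under Protocol Compliance, "Deviations from the overall study protocol which are found to frequently recur are not acceptable". As the criteria stand, each correct enrolment departs from the written rule.

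For the follow-up, the report would describe maintenance of change on the primary outcome at six weeks when both timing instructions deliver about five.

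For travel, a screener working from the Study Summary and one working from the inclusion list would apply different entry rules.

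**Working it through.** **1. Exclusion criteria: literal effect against stated reason**

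| Item | Literal effect under the exclusion heading | What the stated reason targets | Agree? |
|---|---|---|---|
| 1 | Excludes low MoCA scores | Cognitive deficit that cannot be accommodated | Yes |
| 2 | Excludes Cluster 8 or below | Clusters above 8 | No |
| 3 | Excludes insufficient English | Need for an interpreter | Yes |
| 4 | Excludes those with no other therapy | Those having other therapy | No |

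Two of four are inverted. No other section corrects this. The Study Summary's eligibility row mentions neither cluster nor concurrent therapy, and the screening text in the Study Regimen refers back to the inclusion and exclusion criteria.

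**2. Follow-up interval**

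Inputs from the Schedule of Procedures: session 1 at week 4, session 12 at week 15, Change Interview at week 16, follow-up at week 20. Stated interval: six weeks after therapy = 6 × 7 = 42 days.

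- Check on the schedule: week 4 + 11 weekly steps = week 15, so the placing of session 12 is reproduced.
- Schedule interval: 20 − 15 = 5 weeks = 35 days. Shortfall: 42 − 35 = 7 days; 7/42 = 16.7%.
- Text interval: 7 days to the Change Interview plus one month. The length of a month is not defined, so a range is shown:

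| Month | Days after last session | Weeks | Shortfall in days | Shortfall |
|---|---|---|---|---|
| 28 days | 35 | 5.00 | 7 | 16.7% |
| 30 days | 37 | 5.29 | 5 | 11.9% |
| 31 days | 38 | 5.43 | 4 | 9.5% |

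The schedule and the text agree with each other, and neither gives six weeks. Six weeks after week 15 is week 21. Week 20 is six weeks after week 14, the week of session 11, which is not the end of therapy.

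The schedule row names only symptom and process measures. That the OPQOL-brief falls at this visit comes from the Table of Outcomes.

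**3. Travel and in-person contact**

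- Study Summary: ability to travel is required. Inclusion Criteria: not required.
- Study Setting: therapy is by telephone or videocall. Assessment and Management of Risk: therapy may be face-to-face or remote.
- Study Regimen: the Change Interview may be in person or remote, depending on restrictions. Participant Payment: travel to it is reimbursed if distancing is relaxed. Assessment and Management of Risk: participants must come in for it.

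**4. Sample size.** Three cases allowing for 25% dropout: 3/(1 − 0.25) = 4, which reproduces the plan's maximum of four. None of the points above affects it.

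**The case against.** The strongest reply is that nothing will go wrong in practice. The reasons printed beside items 2 and 4 make the intent plain, one role (the Field Research Supervisor) does the screening, and cluster ratings already exist as routine data. At most four people are enrolled, and nobody is likely to log an enrolment that matches the printed reason as a deviation. The negative wording may simply be inclusion criteria placed under the wrong heading. All of this is fair and limits the consequence. It does not make the operative text right.

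On the follow-up, it can be said that Tables 1 and 2 define no analysis that depends on the interval, that only the Study Regimen ties the label to the end of therapy, and that the call would be made at a consistent time for every participant. The first and third points stand, so no stated calculation changes. Counting weeks 15 to 20 inclusively as six does not rescue the label, because the same documents treat week 15 to week 16 as one week. Flexible therapy length does not rescue it either: the text rule runs from the final session whenever that falls. It is true that the schedule gives week numbers and not days, so 35 days is nominal.

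On travel, the summary item may be left over from face-to-face delivery, and the risk section describes burden in general terms. That point is minor.

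**Conclusion.** The concern holds. Two of the four exclusion criteria, as worded, contradict their own reasons and would select the wrong clients if followed exactly. That the negations are drafting slips is an inference, but the adjacent reasons support it strongly. The follow-up on the primary outcome is 35 days after therapy by the schedule and 35 to 38 days by the text, against 42 stated: 4 to 7 days, or about 10–17%, short. This takes a month as 28 to 31 days and the last session as session 12 or whichever session ends therapy.

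The practical effect is limited: wrong enrolment is unlikely, the pre-, mid- and post-therapy comparisons are untouched, and no planned analysis uses the follow-up interval. The corrections should still be made, because these are entry rules and a time point of the primary outcome. The travel mismatch is minor.

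**What to change.** - **Exclusion criteria.** Delete the opening negation from items 2 and 4, so that item 2 names a rating above Cluster 8 and item 4 names current receipt of another therapy. Each then matches its printed reason.
- **Follow-up.** Either call it a five-week follow-up throughout, or place the call six weeks after the final session (week 21 on the standard schedule). Make the Table of Outcomes, the Study Regimen and the Schedule of Procedures agree, and state the anchor as the final session.
- **Travel.** Reconcile the Study Summary, Study Setting, Inclusion Criteria, Participant Payment, Study Regimen and Assessment and Management of Risk on whether travel is an entry condition and which contacts may be in person.

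The cost is a wording amendment, which the sponsor would classify with the Chief Investigator under Ethics Review and Compliance. If the week-21 option is chosen, up to four calls move by 4 to 7 days, and the sponsor should consider whether the protocol's provision for continuing consent applies.
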